4.3 DOSE

The first 6 subjects will constitute the *Safety Lead-In Cohort* and be assigned to cabozantinib 40 mg PO daily for 4 weeks, followed by a 2 week drug washout period before prostatectomy. The remaining subjects will be randomized to either: (1) cabozantinib 40 mg PO daily for 4 weeks, followed by a 2 week drug washout period before prostatectomy (n = 14), or (2) immediate prostatectomy (n = 10). The dose of cabozantinib is based on information from both the dose escalation and phase II randomized discontinuation trials in mCRPC patients.⁴¹ This dose escalation trial by Smith et al. indicated that the impressive bone scan changes are demonstrated at the 40 mg dose with better tolerability that reported at the 100 mg dose. Because of this and the relatively high number of dose reductions and grade 3 adverse events on the phase III trial (COMET-1),¹² we believe that the 40 mg dose may have a more favorable risk-benefit ratio in the population of men with localized prostate cancer. The minimum two week washout period is based on both cabozantinib's terminal half-life of approximately 120 hours (cabozantinib [XL-184] IB, Version 9.0) and extrapolation from neoadjuvant trials of anti-angiogenic agents in renal cell carcinoma.^{42,43}

4.4 PROSTATECTOMY

Subjects will undergo a radical prostatectomy as part of their routine medical care at Day 43 (Arm A, cabozantinib) or Day 1 (Arm B, immediate prostatectomy). The surgeon must plan to use robotic or laparoscopic techniques with a low risk for conversion to open prostatectomy, in the opinion of the treating surgeon.

4.5 DEFINITION OF EVALUABLE SUBJECTS

Arm A subjects must complete 21 out of 28 days of planned cabozantinib dosing and proceed to prostatectomy within 14 (+3) days of their last dose of cabozantinib in order to be evaluable for this study's endpoints. Arm B subjects must receive a prostatectomy in order to be evaluable. Subjects who are not evaluable will be replaced.

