Endpoints:	
Primary: Apoptotic index by cleaved caspase-3
 
Secondary: Description of immune biomarkers, including:
 
 • Immune phenotyping of paired peripheral blood and tumor tissue: Myeloid-derived suppressor cells (MDSCs), neutrophils, M1 macrophages, and M2 macrophages in tumor tissue • Immunohistochemical (IHC) analysis of CD8+, programmed death ligand-1 (PD-L1), cytotoxic T-lymphocyte-associated protein 4 (CTLA-4), interleukin-1 receptor antagonist (IL-1RA) and B7H3 in tumor tissue • Neutrophil chemotactic factors (CXCL12 and HMGB1) and MDSC-promoting cytokines (CCL5, CCL12, CD40) in tumor tissue 
Exploratory:
 
 1. Rates of pCR and \leqpT2 2. Relapse-free survival rate at 3 years 3. Quantification of TUNEL, Ki-67, and CD31 staining 4. Quantification of c-MET, VEGF, HGF, and activated c-MET in prostatectomy tissue 5. Correlation of vimentin, AR, SNAIL, AXL, and N-cadherin with cabozantinib exposure 6. Measurement of PTEN and p53 genomic and protein expression status in tumor tissue 7. Adverse events by CTCAE v5.0, dose intensity of cabozantinib 8. Blood loss at prostatectomy and duration of hospital stay 9. Angiome biomarkers 10. Gene expression patterns using RNA sequencing 11. Serum and intratumoral androgen concentrations 12. Alterations in cfDNA
Study Population:	Eligible patients will have histologic evidence of adenocarcinoma of the prostate and be deemed candidates for curative radical prostatectomy. They will have intermediate-or high-risk, clinically localized disease and have not received prior treatment for prostate cancer.
Phase:	Phase II
Description of Sites/Facilities Enrolling Participants:	This is a multicenter study of 30 evaluable subjects. Duke is the lead site for this trial. Subjects who do not receive 21 out of 28 days of planned study drug administration and proceed to radical prostatectomy within 14 (+3) days of their last dose of study drug (Arm A only) or do not proceed to radical prostatectomy (Arm B only) will be replaced. There will be a second site selected TBD.
Description of Study Intervention:	Patients will be assigned (Safety Lead-In Cohort) or randomized to either: (1) cabozantinib 40 mg PO daily for 4 weeks, followed by a 2 week drug

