4. To measure expression levels of c-MET, VEGF, and HGF, as well as activation status of c-MET in prostate tissue.	4. Quantification of c-MET, VEGF, HGF, and activated c-MET in prostatectomy tissue	4. To evaluate effects on the c-MET/HGF axis.
5. To describe changes in plasticity signaling markers associated with prostate tumors, including vimentin, AR, SNAIL, AXL, and N-cadherin, with cabozantinib exposure	5. Correlation of changes in vimentin, AR, SNAIL, AXL, and N-cadherin with cabozantinib exposure	5. To describe effects on markers of epithelial-mesenchymal transitions (EMT).
6. To evaluate PTEN and p53 genomic and protein expression status in tumor tissue	6. Measurement of PTEN and p53 genomic and protein expression status in tumor tissue	6. To evaluate whether cabozantinib may be more active in a subset of pTEN/p53-deficient tumors. ¹⁰
7. To demonstrate that cabozantinib is safe and tolerable in patients	7. Adverse events by CTCAE v5.0, dose intensity of cabozantinib.	7. To demonstrate that cabozantinib is safe and tolerable in patients

OBJECTIVES	ENDPOINTS	JUSTIFICATION FOR ENDPOINTS
undergoing radical prostatectomy.		undergoing radical prostatectomy.
8. To demonstrate that surgery is safe and feasible in patients undergoing treatment with cabozantinib.	8. Blood loss at prostatectomy and duration of hospital stay.	8. To demonstrate that surgery is safe and feasible in patients undergoing treatment with cabozantinib.
9. To collect plasma angiome samples (multiplex ELISA) for analysis and correlation with primary and key secondary endpoints.	9. Angiome biomarkers.	9. To collect samples for possible later analysis and correlation with key endpoints
10. To describe gene expression patterns (in particular those associated with apoptosis, androgen receptor signaling, c-MET activation, and a c-MET-specific endocytosis panel) correlated with cabozantinib administration using RNA sequencing analysis.	10. Gene expression patterns.	10. To collect samples for possible later analysis and correlation with key endpoints.
11. To explore changes in serum and intratumoral androgen concentrations related to cabozantinib treatment.	11. Serum and intratumoral androgen concentrations.	11. To collect samples for possible later analysis and correlation with key endpoints.12

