7.4 CABOZANTINIB DOSE MODIFICATIONS, INTERRUPTIONS, AND DISCONTINUATION

The following should be taken into consideration in decisions regarding dose modifications (reductions or interruption):

- As a general approach all AEs should be managed with supportive care at the earliest signs of toxicity considered related to the study treatment. Should this be ineffective, dose interruptions and/or reductions should be considered to prevent worsening of toxicity.
- The assigned starting dose for cabozantinib is 40 mg/day. One dose reduction level of cabozantinib to 20 mg/day is permitted (see Table 7-2).
- Dose modification criteria for cabozantinib are shown in Table 7-3. Dose interruptions and/or reductions should be implemented for unacceptable toxicity. Doses may be modified at any time while a subject is on treatment.
- Dose reductions or interruptions may also occur in the setting of lower grade toxicity than defined in Table 7-3, if the investigator feels it is in the interest of a subject's safety and will optimize drug tolerability.
- Interruption of cabozantinib treatment for cabozantinib-related AEs may occur at any time per investigator discretion. If treatment is interrupted due to related AEs for more than 1 week, cabozantinib should be discontinued unless there is unequivocal evidence that the subject is benefitting. In this situation, a subject may be able to restart therapy with a dose reduction upon resolution of the toxicity per the discretion of the investigator.

Guidelines for the management of specific AEs are provided in Section 7.4.2.

Table 7-2: Dose Reductions of Cabozantinib

Assigned Dose	First Dose Level Reduction	Second Dose Level Reduction
40-mg cabozantinib oral qd	20-mg cabozantinib oral qd	No dose reduction permitted

Cabozantinib will be discontinued if a daily dose of 20-mg cabozantinib (minimum dose) is not tolerated

Table 7-3: Dose Modifications of Cabozantinib for Treatment-Related AEs

CTCAE v.5.0 Grade	Recommended Guidelines for Management ^a
Grade 1 AEs	Add supportive care as indicated. Continue cabozantinib treatment at the current dose level if AE is manageable and tolerable.
Grade 2 AEs which are tolerable and are easily managed	Continue cabozantinib treatment at the current dose level with supportive care.

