7.4.2 GUIDELINES FOR MANAGEMENT OF POTENTIAL ADVERSE EVENTS

Subjects on Arm A receiving cabozantinib will be monitored for AEs from the time of taking the first dose of study drug through their last follow-up visit (30 days after the date of the last dose of cabozantinib treatment). Subjects will be instructed to notify their physician immediately at the onset of any AE. Seriousness, severity grade, and relationship to study treatment of AEs will be determined by the investigator. AE severity will be graded by the investigator in accordance with CTCAE v.5.0.

Management of severe or intolerable adverse reactions may require temporary dose reduction and/or interruption for cabozantinib.

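### Section 4.5 applies the Arm A completer-and-window filter to all study endpoints, and no all-treated population is named for the final AE, dose-intensity and surgical summaries (minor)

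*Combined protocol and SAP*

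**What the plan says.** Section 4.5 (Definition of Evaluable Subjects) sets a condition for Arm A: each man "must complete 21 out of 28 days of planned cabozantinib dosing and proceed to prostatectomy within 14 (+3) days of their last dose". The section states the purpose of this condition as "in order to be evaluable for this study's endpoints". It adds: "Subjects who are not evaluable will be replaced". Nothing limits the condition to the primary or the tissue endpoints.

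The table in Section 3 lists, as exploratory endpoint 7, "Adverse events by CTCAE v5.0, dose intensity of cabozantinib" and, as exploratory endpoint 8, "Blood loss at prostatectomy and duration of hospital stay". The matching objectives are to demonstrate that the drug is tolerable before prostatectomy and that surgery after it is safe and feasible.

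The Data Analysis paragraph of Section 11.1 covers the apoptosis, proliferation and microvessel indices, pCR and pT2, angiome, gene expression, cfDNA, mesenchymal markers and androgens. It gives neither a method nor a population for AEs, dose intensity, blood loss or hospital stay. No safety, all-treated or intention-to-treat set is defined; ITT appears only in the abbreviation list.

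Other parts of the plan do use all treated men. Section 7.4.2 says that Arm A subjects "will be monitored for AEs from the time of taking the first dose of study drug". The stopping rules in Sections 4.1 and 11.1 count subjects who received cabozantinib. The reports in Section 10.3, after 6, 12 and 18 such subjects, cover every AE on study.

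**The concern.** The filter is linked to the outcomes that endpoints 7 and 8 are meant to describe. A man who stops the drug for toxicity before his twenty-first dosing day fails it. So does a man whose operation is delayed past the window or never takes place. If the Section 4.5 set were used for the final summaries, the men who tolerated the drug worst would be removed and replaced by men who completed it. Every Arm A man left in the table would have taken at least 21 days and had surgery on time, by construction. Such a table could not show failure to tolerate the drug or failure to reach surgery as planned, which is what objectives 7 and 8 need it to be able to show.

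**Working it through.** **Inputs.** Filter: at least 21 of 28 days, surgery within 14 (+3) days (Section 4.5). Evaluable numbers: 20 cabozantinib, 10 control; up to 33 enrolled for 30 evaluable; 70% power at 1 SD and 96% at 1.5 SD, two-sided 0.05 (Section 11.1). Dose levels: 40 mg and 20 mg; discontinuation after a related hold of more than one week (Section 7.4).

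**1. The plan's own power.** Two-sample t-test, df = 10 + 20 - 2 = 28. Noncentrality = d / sqrt(1/10 + 1/20), which is 2.58 for d = 1. Noncentral-t power is 70.3% at 1 SD and 96.2% at 1.5 SD, matching the stated 70% and 96%. These figures depend on the evaluable set for the primary endpoint, which this point leaves alone.

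**2. Which toxicities the filter removes.** Section 7.4 says "If treatment is interrupted due to related AEs for more than 1 week, cabozantinib should be discontinued", unless the subject is unequivocally benefiting. A hold of 8 days or more leaves at most 28 - 8 = 20 days, below 21, assuming that missed days are not made up after Day 28. A hold of exactly 7 days leaves 21, so that man stays evaluable. So do men reduced to 20 mg and men who stop after 21 days, provided that surgery is in window. The filter therefore removes early stoppers and out-of-window or absent surgery, not toxicity in general.

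**3. Dose intensity.** The plan does not define the measure. In days, the lowest value in the evaluable set is 21/28 = 75%. In milligrams it could be lower because reductions are kept: 21 x 20 / (28 x 40) = 420/1120 = 37.5% as a bound.

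**4. AE rates, illustration only.** Allowed replacements: 33 - 30 = 3 across both arms, so the Arm A number k could be 0. Assume k = 1, 2 or 3 treated Arm A men are non-evaluable and each had the AE of interest.

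| Events in the 20 evaluable men | Evaluable only | All treated, k = 1 | k = 2 | k = 3 |
|---|---|---|---|---|
| 0 | 0/20 = 0% | 1/21 = 4.8% | 2/22 = 9.1% | 3/23 = 13.0% |
| 2 | 2/20 = 10% | 3/21 = 14.3% | 4/22 = 18.2% | 5/23 = 21.7% |

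Exact 95% intervals for the first row: 0 to 16.8%, 0.1 to 23.8%, 1.1 to 29.2% and 2.8 to 33.6%. They overlap widely. With k = 0 the two populations agree.

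**5. Would the stopping rules end the trial first?** Assume that all k early stops are AE-related, and hence DLTs, that they fall in random order among 20 + k treated men, and that there are no other DLTs. The rules are 2 or more DLTs in the first 6, or 3 or more in the first 12.
- k = 1: 0%.
- k = 2: C(6,2)/C(22,2) = 15/231 = 6.5%.
- k = 3: two or more in the first 6 gives 15 x 17 + 20 = 275 arrangements. All three in the first 12 but at most one in the first 6 gives 220 - (15 x 6 + 20) = 110. Total 385 of C(23,3) = 1771, or 21.7%.

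On these assumptions the trial would usually go on to its final tables.

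**The case against.** The strongest reply is that the filter was never meant for safety. The synopsis uses it only for replacement: men are replaced if they fall among "Subjects who do not receive 21 out of 28 days of planned study drug administration" or miss the surgery window. In Section 11.1, evaluable is tied to the t-test sample size and the over-enrolment allowance. Every AE population that the plan does use is all-treated: capture from the first dose, DLT counts and the three periodic reports. An AE that permanently stops the drug is a DLT and remains countable whether or not the man is evaluable. The endpoints are exploratory, and the plan describes a hypothesis-generating study with a sample size of convenience.

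Most of this stands. Tissue evaluability is the likely intent, and no sentence directs a filtered safety table. But the all-treated passages govern collection, monitoring and stopping. None sets the population for the final endpoint summaries, and none covers dose intensity, blood loss or hospital stay. For those, Section 4.5 is the only population rule, and its wording reaches them.

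A reader might also infer that data from replaced men would be lost. The documents do not support that. Section 6 collects tissue at prostatectomy on both arms, Section 6.13 has the Arm A hospital course reviewed, and Section 6.15 follows both arms for 3 years. None of these is limited to evaluable men, and Section 6.16 does not list non-evaluability as a reason to discontinue a subject.

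**Conclusion.** The point holds as a minor one, with medium confidence. Followed as written, Section 4.5 would give a biased final picture of tolerability and surgical feasibility, with dose intensity cut off at about 75% of planned days. The size depends on how many treated Arm A men turn out non-evaluable, which the plan cannot know. The assumed range of 1 to 3 moves an AE rate by about 4 to 13 percentage points, and 0 moves it not at all.

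Two stronger readings are tempting and are not supported. One is that patient safety monitoring is compromised: it is not, because it already runs on all treated men. The other is that the primary comparison is flawed: the evaluable set suits a pharmacodynamic t-test on tissue exposed to the drug, and an additional analysis of the primary in a wider set would be a matter of preference. Nor does the point call for comparing blood loss and hospital stay with Arm B. Objective 8 concerns cabozantinib-treated men, and the Arm B schedule has no post-operative visit or hospital-course review.

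**What to change.** In Section 4.5, limit the evaluable set to the tissue endpoints and the replacement rule. In Section 11.1, add two sentences:

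- AEs, dose intensity, and whether and when surgery took place are summarised in all subjects who received at least one dose of cabozantinib, including those later replaced.
- Blood loss and hospital stay are summarised in all cabozantinib-treated subjects who had surgery, whatever their number of doses or the timing of the operation.

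The cost is a few sentences. The plan's existing collection already applies to replaced men, so no new visit or sample is needed. The downside is that tolerability figures may look slightly less favourable. The primary t-test, its evaluable set and its stated 70% power stay as they are.

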	washout period before prostatectomy (n = 20), or (2) immediate prostatectomy within 12 weeks of registration (n = 10). The Safety Lead-In Cohort will consist of 6 subjects receiving cabozantinib prior to prostatectomy. The randomized portion will consist of the remaining cabozantinib prior to prostatectomy subjects (n=14) and immediate prostatectomy subjects (n=10).
Study Duration:	We estimate an accrual period of 1 year, with last patient last visit at 22 months and final report at 25 months.
Participant Duration:	Screening Phase: Six weeks (42 days) Treatment Phase (including prostatectomy) 
 • Arm A (cabozantinib): up to 85 days • Arm B (immediate prostatectomy): 1 day Follow-up Phase: 3 years post-prostatectomy for relapse-free survival

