Sample Size Justification. The primary endpoint of this randomized phase II study is the apoptotic index by cleaved caspase-3 in prostatectomy specimens following 4 weeks of treatment with cabozantinib compared with prostatectomy specimens of untreated patients. The target sample size of convenience is 30 patients where the randomization allocation ratio will be 2:1 cabozantinib-to-control. The randomization will not be stratified on any variable. The null hypothesis is that the mean apoptotic indices are equal between the two groups. The percent of tumor cells positive for cleaved caspase 3 staining for each patient will be evaluated for the primary objective. The 6 subjects assigned during the Safety Lead-In Cohort are included in the 30 patient sample size and 2:1 randomization allocation ratio.

Based on data from a prior, unpublished pre-prostatectomy study of sunitinib, we expect the controls to have minimal staining (i.e., $\leq 5\%$). In the proposed study we will enroll 10 controls and 20 cabozantinib-treated patients to demonstrate increased staining (i.e., $>5\%$). A two sample t-test will be used to compare group means. With 10 and 20 evaluable patients in the control and cabozantinib-treated groups, respectively, the test will provide 70% power to detect a mean (for positive tumor cells percentage) difference of one-fold standard deviation based on a two-sided type I error of 0.05; or 96% power to detect an one-and-half fold standard deviation difference. Assuming a 10% unevaluable rate, we will enroll up to 33 patients total to have 30 evaluable patients.

Data Analysis. Box plots and statistical summaries of apoptotic (cleaved caspase-3, TUNEL), proliferation (Ki-67), and MVD (CD31) indices will be presented. In addition, the t-test will be used to compare the two arms on apoptotic index, proliferation and MVD indices. Further, the Chi-square test will be used to compare the two treatment arms on pathologic complete response rate (pCR) and pathologic T2 (pT2) rate. The angiome, gene expression, cell-free DNA and mesenchymal markers analyses will be reported descriptively as the trial's limited sample size will not permit definitive analyses for these exploratory objectives. The t-test will be used to compare the two arms' serum and tissue androgen and androgen precursor levels.

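### The primary comparison is a per-protocol analysis with dosing and surgery-timing exclusions in Arm A only, and no analysis of all men with a specimen stands beside it

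*Combined protocol and SAP*

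**What the plan says.** Section 4.5 sets different conditions by arm. For the treated arm: "Arm A subjects must complete 21 out of 28 days of planned cabozantinib dosing and proceed to prostatectomy within 14 (+3) days" of the last dose, "in order to be evaluable for this study's endpoints". For the control arm: "Arm B subjects must receive a prostatectomy in order to be evaluable. Subjects who are not evaluable will be replaced". The scope is the study's endpoints as a whole, so the primary endpoint is covered.

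The Synopsis (1.1) repeats the rule. In Arm A it replaces "Subjects who do not receive 21 out of 28 days of planned study drug administration" and have surgery in the window. In Arm B it replaces only those who "or do not proceed to radical prostatectomy (Arm B only) will be replaced". The Synopsis gives Arm B a 12-week limit from registration to surgery, but that limit is not a condition of evaluability.

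Section 11.1 states the power of the two-sample t-test "With 10 and 20 evaluable patients in the control and cabozantinib-treated groups, respectively". It assumes 10% unevaluable and allows up to 33 enrolled to reach 30. It defines no analysis of all assigned or all operated men. Intention-to-treat appears only in the abbreviation list (Section 15).

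Three other places matter:

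- Section 4.4 describes prostatectomy as routine care.
- Section 6 has tissue collected at prostatectomy in both arms and does not limit this to evaluable men.
- Section 11.1 counts the six lead-in men, who are assigned and not randomised, among the 20 treated men.

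**The concern.** The Arm A conditions are met or failed after assignment, and failing them can be a consequence of the drug. Section 7.4 says that an interruption of more than one week for related adverse events should generally lead to discontinuation. The 21-of-28 rule leaves 28 − 21 = 7 days of slack, so such a man who stops before day 21 becomes unevaluable. Sections 4.1 and 11.1 also count any adverse event that leads to permanent discontinuation as a dose-limiting toxicity. One event can thus be a safety outcome and also remove the man from the primary comparison. No dosing or timing filter acts on Arm B.

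If tolerance is related to tumour biology, frailty or exposure, the evaluable Arm A men differ from the Arm A men who were assigned, while the controls are not selected in this way. The difference in cleaved caspase-3 would then mix a drug effect with a selection effect, and the planned report gives no means of telling them apart. The data to check this would largely exist, because a man who stops early or is operated on late still yields a specimen.

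**Working it through.** **Inputs from Section 11.1.** 10 control and 20 treated evaluable men; two-sample t-test; two-sided α = 0.05; 10% unevaluable; at most 33 enrolled. **Assumed, because the documents give no figure:** the difference in mean index between excluded and retained Arm A men, and the drug effect in excluded men.

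**1. Reproduce the plan's power.** Noncentrality = d / √(1/10 + 1/20) = d / 0.3873, with 28 degrees of freedom and critical value 2.048.
- d = 1.0 SD: noncentrality 2.582, power 70.3% (plan: 70%).
- d = 1.5 SD: noncentrality 3.873, power 96.2% (plan: 96%).

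The stated power is right, and it belongs to the evaluable set.

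**2. Bias from one-arm exclusion when the drug has no effect.** Let p be the share of Arm A excluded, R the mean of retained men and E the mean of excluded men. The full-arm mean is (1 − p)R + pE, so the retained mean is off by R − [(1 − p)R + pE] = p(R − E). Take |R − E| = 1 SD.
- p = 10%: bias 0.10 SD, noncentrality 0.10 / 0.3873 = 0.258, two-sided rejection 5.7%.
- All 33 − 30 = 3 spare men are Arm A exclusions: p = 3/23 = 13%, bias 0.13 SD, rejection 6.2%.

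**3. A second model as a range.** Suppose the least tolerant 10% are excluded and tolerance correlates ρ with the index (ρ assumed). The shift is ρ × φ(z) / (1 − p), where z is the p-quantile of the standard normal; at p = 10% this is ρ × 0.195 SD.

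| ρ | Shift (SD) | Two-sided error |
|---|---|---|
| 0.3 | 0.06 | 5.2% |
| 0.5 | 0.10 | 5.7% |
| 1 | 0.19 | 7.8% |

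**4. Power of an all-specimen comparison.** With three extra Arm A men the comparison is 10 v 23. If those three carry none of a 1 SD effect, the Arm A mean effect is 20/23 = 0.87 SD.
- Noncentral t at 0.87 SD, 10 v 23: 60%.
- Simulation of the actual mixture (40,000 runs), which also carries the added spread: 57%.
- Simulation if the three keep half the effect: 66%; if they keep all of it: 73%.

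**5. Randomised men only, as planned (14 v 10).** Noncentral t with 22 degrees of freedom: 63.6% at 1 SD and 93.3% at 1.5 SD.

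**The case against.** The best defence is that an exposed-and-evaluable set suits the question. Section 2.2 presents the study as hypothesis-generating, and Section 11.1 defines the primary endpoint in specimens taken after four weeks of cabozantinib. The rule is prespecified and openly stated. It also selects on tolerance less sharply than it may seem: it counts days and not dose, so a man reduced to 20 mg stays evaluable; up to seven days may be missed; and late surgery can have scheduling causes. All of this stands. It justifies keeping the evaluable-set test, but not leaving it as the only primary-endpoint analysis, unlabelled.

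A reader might also infer three stronger points that the documents do not support.

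- *That replacements are placed directly in Arm A.* Section 6.5 has every eligible, approved subject randomised except the lead-in men, with no exception for replacements.
- *That exclusions could reach the 33% adverse-event discontinuation rate that Section 2.1 cites for the phase III trial.* Keeping 20 evaluable men at that rate needs 20 / 0.67 ≈ 30 in Arm A and about 40 in all, above the cap of 33. The rate comes from heavily pre-treated metastatic patients, and Section 4.3 gives that trial's tolerability as a reason for the 40 mg choice.
- *That a full intention-to-treat analysis is being withheld.* Men never operated on have no specimen, so the widest feasible set is all men with one.

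**Conclusion.** The point holds as a matter of analysis set and labelling. The only primary comparison that the plan defines is per-protocol, with dosing and timing exclusions in one arm that can follow from toxicity. At the planned unevaluable rate the distortion is modest: a two-sided error of about 5.7% with 10% excluded, or 6.2% at 3/23, in place of 5%. Both figures rest on the assumed 1 SD gap; at 10% excluded the correlation model gives 5.2% to 7.8%. The direction is unknown, so selection could as easily hide an effect as create one. The stated power is correct for the set to which it applies. Because six of the 20 treated men are not randomised, the comparison is not fully randomised even before any exclusion, and an added analysis has to say how it treats them.

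**What to change.** In Section 11.1:

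1. Label the evaluable-set t-test as per-protocol.
2. Prespecify a supplementary comparison of the primary endpoint in all men with a prostatectomy specimen, in the arm to which they were assigned or randomised, whatever their dosing or surgery date. State that the six lead-in men are included.
3. Show beside it a version restricted to randomised men (14 v 10 as planned).
4. Report exclusions from the evaluable set by arm, with reasons.

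The supplementary result is there to be read beside the main one. A rule that both must agree before any claim is made is a matter of preference and is not needed.

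The cost is some added wording and staining of a few specimens that Section 6 already has collected. The statistical downside is dilution by men who had little drug: about 57% to 60% power at 1 SD if 3 of 23 carry no effect, against 70% for the evaluable set. The randomised-only version has 63.6%. No dose, schedule or clinical rule changes.
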